10.2. Appendix 2: Clinical Laboratory Tests

- The tests listed in Table 2 will be performed as described in the Laboratory Manual.
- Protocol-specific requirements for the inclusion and exclusion of participants are detailed in Section 5.1 and Section 5.2, respectively.
- Additional tests may be performed during the study as determined necessary by the investigator or required by local regulations.
- Investigators must document their review of each laboratory safety report.

Table 2: Protocol-Required Laboratory Tests

Laboratory Test		Paramete	ers
Hematology	RBC count platelet count hemoglobin hematocrit	RBC indices: MCV MCH	WBC count with differential: neutrophils eosinophils lymphocytes basophils monocytes
Serum chemistry	ALT AST albumin ^a BUN	creatinine glucose potassium chloride bicarbonate	sodium total protein ^a calcium bilirubin (total and direct)
Routine urinalysis		blood, ketones, bilirubin, u	urobilinogen, nitrite, leukocyte esterase abnormal)
Pregnancy testing	time points (as needed A high FSH level in t postmenopausal state	d for WOCBP potential, de he postmenopausal range i	onal contraception or hormonal
Specialty laboratory tests	C-reactive protein	ESR	TSH
Other screening tests	10.2.1.3, and Section	CV, HIV (see exclusion or 10.2.1.4, respectively)	riterion 7 and Sections 10.2.1.2,

ALT=alanine aminotransferase; AST=aspartate aminotransferase; BUN=blood urea nitrogen; ESR=erythrocyte sedimentation rate; FSH=follicle-stimulating hormone; hCG=human chorionic gonadotropin; HBV=hepatitis B virus; HCV=hepatitis C virus; MCH=mean corpuscular hemoglobin; MCV=mean corpuscular volume; RBC=red blood cell; TSH=thyroid stimulating hormone; WBC=white blood cell; WOCBP=women of childbearing potential a Results will be blinded.

10.2.1. Other Screening Tests

10.2.1.1. SARS-CoV-2

A SARS-CoV-2 nasopharyngeal swab test will be performed on all participants at screening; individuals with positive test results are excluded from participating in the study (Section 5.2, exclusion criterion 6).

Additional COVID-19 testing recommendations/guidelines are presented in Section 10.5.

10.2.1.3. Hepatitis C Virus

Participants with an active acute or chronic hepatitis C viral infection at screening cannot be randomized in the study. The hepatitis C virus antibody serologic test will identify an active hepatitis C viral infection as indicated in Table 4.

Table 4: Interpretation of the Hepatitis C Antibody Test

HCV antibody test result	Interpretation
Positive	The patient cannot be randomized in the study because the test results indicate an active acute or chronic HCV infection unless associated with a negative HCV RNA test

HCV=hepatitis C virus

10.2.1.4. Human Immunodeficiency Virus

Individuals who are HIV positive are not eligible for this study.

^a This decision will be made by a medical physician with enough experience in hepatology or infectious disease. Additional tests (eg, HBV viral load) could be required to determine the patient's status.

10.3. Appendix 3: AEs and SAEs: Definitions and Procedures for Recording, Evaluating, Follow up, and Reporting

10.3.1. Definition of AE

AE Definition

- An AE is any untoward medical occurrence in a clinical study participant, temporally associated
 with the use of IMP, whether or not considered related to the IMP.
- NOTE: An AE can therefore be any unfavorable and unintended sign (including an abnormal laboratory finding), symptom, or disease (new or exacerbated) temporally associated with the use of IMP.

Events to be Collected as AEs

- Any abnormal laboratory test results (hematology, clinical chemistry, or urinalysis) or other safety assessments (eg, ECG, radiological scans, vital sign measurements), including those that worsen from baseline, considered clinically significant in the medical and scientific judgment of the investigator (ie, not related to progression of underlying disease)
- Exacerbation of a chronic or intermittent pre-existing condition including either an increase in frequency and/or intensity of the condition
- New condition detected or diagnosed after IMP administration even though it may have been present before the start of the study
- Signs, symptoms, or the clinical sequelae of a suspected intervention-intervention interaction
- Signs, symptoms, or the clinical sequelae of a suspected overdose of either IMP or a
 concomitant medication. Overdose per se will not be reported as an AE/SAE unless it is an
 intentional overdose taken with possible suicidal/self-harming intent. Such overdoses should be
 reported regardless of sequelae
- Lack of efficacy or failure of expected pharmacological action per se will not be reported as an AE or SAE. Such instances will be captured in the efficacy assessments. However, the signs, symptoms, and/or clinical sequelae resulting from lack of efficacy will be reported as AE or SAE if they fulfill the definition of an AE or SAE

Events NOT to be Collected as AEs

- Any clinically significant abnormal laboratory findings or other abnormal safety assessments
 that are associated with the underlying disease, unless judged by the investigator to be more
 severe than expected for the participant's condition
- The disease/disorder being studied or expected progression, signs, or symptoms
 of the disease/disorder being studied, unless more severe than expected for the participant's
 condition
- Medical or surgical procedure (eg, endoscopy, appendectomy): the condition that leads to the procedure is the AE
- Situations in which an untoward medical occurrence did not occur (social and/or convenience admission to a hospital)
- Anticipated day-to-day fluctuations of pre-existing disease(s) or condition(s) present or detected at the start of the study that do not worsen

10.3.2. Definition of SAE

An SAE is Defined as Any Untoward Medical Occurrence That, at Any Dose:

a. Results in death

b. Is life threatening

The term *life threatening* in the definition of *serious* refers to an event in which the participant was at risk of death at the time of the event. It does not refer to an event that hypothetically might have caused death if it were more severe.

c. Requires inpatient hospitalization or prolongation of existing hospitalization

- In general, hospitalization signifies that the participant has been admitted to the hospital or
 emergency ward for observation and/or treatment that would not have been appropriate in the
 physician's office or outpatient setting. Complications that occur during hospitalization are AEs.
 If a complication prolongs hospitalization or fulfills any other seriousness criteria, the event will
 be considered serious. When in doubt as to whether hospitalization occurred or was necessary,
 the AE should be considered serious.
- Hospitalization for elective treatment of a pre-existing condition that did not worsen from screening will not be collected as an AE.

d. Results in persistent or significant disability/incapacity

- The term disability means a substantial disruption of a person's ability to conduct normal life functions.
- This definition is not intended to include events of relatively minor medical significance such as uncomplicated headache, nausea, vomiting, diarrhea, influenza, and accidental trauma (eg, sprained ankle) that may interfere with or prevent everyday life functions but do not constitute a substantial disruption.

e. Is a congenital anomaly/birth defect

f. Other situations:

- Medical or scientific judgment should be exercised by the investigator in deciding whether SAE
 reporting is appropriate in other situations such as significant medical events that may
 jeopardize the participant or may require medical or surgical intervention to prevent one of the
 other outcomes listed in the above definition. These events should usually be considered serious.
 - Examples of such events include invasive or malignant cancers, intensive treatment for allergic bronchospasm, blood dyscrasias, convulsions or development of intervention dependency or intervention abuse.
- Suspected transmission of any infectious agent via the IMP will also be treated as an SAE.

10.3.3. Recording and Follow Up of AE and/or SAE

AE and SAE Recording

- When an AE/SAE occurs, it is the responsibility of the investigator to review all documentation (eg, hospital progress notes, laboratory reports, and diagnostics reports) related to the event.
- The investigator will then record all relevant AE/SAE information.
- It is **not** acceptable for the investigator to send photocopies of the participant's medical records in lieu of completion of the required form.
- There may be instances when copies of medical records for certain cases are requested. In this
 case, all participant identifiers, with the exception of the participant number, will be redacted on
 the copies of the medical records before submission.
- The investigator will attempt to establish a diagnosis of the event based on signs, symptoms, and/or other clinical information. Whenever possible, the diagnosis (not the individual signs/symptoms) will be documented as the AE/SAE.

Assessment of Severity

The investigator will assess intensity for each AE and SAE reported during the study.

All AEs observed will be graded using the National Cancer Institute (NCI) Common Terminology Criteria for Adverse Events (CTCAE) version 5.0.

The grade refers to the severity of the AE. If a particular AE's severity is not specifically graded by the guidance document, the investigator is to use the general NCI CTCAE definitions of grade 1 through grade 5 following his or her best medical judgment, using the following general guideline:

- Grade 1: Mild; asymptomatic or mild symptoms; clinical or diagnostic observations only; intervention not indicated
- Grade 2: Moderate; minimal, local or noninvasive intervention indicated; limiting ageappropriate instrumental activities of daily living (ADL) (eg, preparing meals, shopping for groceries or clothes, using the telephone)
- Grade 3: Severe or medically significant but not immediately life-threatening; hospitalization or prolongation of hospitalization indicated; disabling; limiting self-care ADL (ie, bathing, dressing and undressing, feeding self, using the toilet, taking medications, and not bedridden)
- Grade 4: Life-threatening consequences or urgent intervention indicated
- Grade 5: Death related to AE

NOTE: An AE that is assessed as severe should not be confused with an SAE. Severe is a category used for rating the intensity of an event; and both AEs and SAEs can be assessed as severe.

An event is defined as "serious" when it meets at least 1 of the predefined outcomes as described in the definition of an SAE, not when it is rated as severe.

Assessment of Causality

- The investigator is obligated to assess the relationship between IMP and each occurrence of
 each AE/SAE as related or not related. The investigator will use clinical judgment to
 determine whether there is reasonable possibility that the IMP caused the AE.
- A reasonable possibility of a relationship conveys that there are facts, evidence, and/or arguments to suggest a causal relationship, rather than a relationship cannot be ruled out.
- Alternative causes, such as underlying disease(s), concomitant therapy, and other risk factors, as
 well as the temporal relationship of the event to IMP administration, will be considered and
 investigated.
- **Related** means that the AE cannot be explained by the participant's medical condition, other therapies, or an accident. The temporal relationship between the AE and IMP administration is compelling and/or follows a known or suspected response pattern concerning that IMP.
- **Not related** means that the AE can be readily explained by other factors such as the participant's underlying medical condition, concomitant therapy, or accident. No plausible temporal or biologic relationship exists between the IMP and the AE.
- The investigator will also consult the Investigator's Brochure (IB) and/or product information, for marketed products, in his/her assessment.
- For each AE/SAE, the investigator **must** document in the medical notes that they have reviewed the AE/SAE and has provided an assessment of causality.
- There may be situations in which an SAE has occurred, and the investigator has minimal
 information to include in the initial report. However, it is very important that the investigator
 always assess causality for every event before the initial transmission of the SAE data.
- The investigator may change his/her opinion of causality in light of follow-up information and send an SAE follow-up report with the updated causality assessment.

 The causality assessment is one of the criteria used when determining regulatory reporting requirements.

Follow up of AEs and SAEs

- The investigator is obligated to perform or arrange for the conduct of supplemental
 measurements and/or evaluations as medically indicated or as requested to elucidate the nature
 and/or causality of the AE or SAE as fully as possible. This may include additional laboratory
 tests or investigations, histopathological examinations, or consultation with other health care
 professionals.
- If a participant dies during participation in the study or during a recognized follow-up period, the investigator will provide a copy of any postmortem findings including histopathology.
- The investigator will submit any updated SAE data within 24 hours of receiving the information.

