5.1. Inclusion Criteria

Participants are eligible to be included in the study only if all of the following criteria apply:

- 1. Reached the age of consent when signing the informed consent form
- 2. Capable of providing signed informed consent, as described in Section 10.1.3, and complying with protocol requirements
- 3. Diagnosed with new-onset POTS post–COVID-19 established by the following:
 - a. History of COVID-19 based on a previous positive test result from either laboratory-confirmed COVID-19 test (eg, a PCR test) or non-laboratory-confirmed COVID-19 test (eg, rapid antigen test); this positive result may be either documented or patient-reported
 - b. Tilt table or orthostatic vital sign measurements during screening consistent with consensus criteria: sustained HR increase of ≥30 bpm within 10 min of standing or head-up tilt (≥40 bpm for individuals aged 18 to 19 years) and/or HR reaching >120 bpm within 10 min; absence of sustained 20 mmHg decrease in systolic blood pressure (SBP)
 - c. Ongoing symptoms of POTS confirmed by the investigator with at least 3 symptoms in each of the following areas lasting longer than 12 weeks after either diagnosis of COVID-19 or after hospital discharge for COVID-19:
 - i. Vasomotor symptoms: fatigue, orthostatic intolerance, brain fog, exertional dyspnea, difficulty with concentration, venous pooling, and exercise intolerance
 - ii. Sympathetic over-compensation symptoms: palpitation, heat intolerance, nausea with or without vomiting, insomnia, anxiety, lack of appetite, chest pain, and diaphoresis
- 4. COMPASS 31 ≥35 at screening
- 5. Agree to use contraceptives consistent with local regulations regarding the methods of contraception for those participating in clinical studies and the following:

Male participants: see Section 10.4.2.2

Female participants of childbearing potential (defined in Section 10.4.1) must have a negative serum pregnancy test at screening and a negative urine pregnancy test at baseline before receiving IMP. Contraceptive requirements are provided in Section 10.4.2.1.

6. Body mass index (BMI) <35 kg/m²

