- Serious TEAEs (IAWK12, IAWK24 and FPA)
- Grade ≥3 TEAEs (IAWK12, IAWK24 and FPA)
- Fatal TEAEs

Document: BIOSdata\argenx\Efgartigimod\HAB40220\Biostatistics\Documentation\SAP

Author: Version Number: 3.0

Version Date: 02 May 2024

Template No.: CS\_TP\_BS016 Revision 7 Reference: CS\_WI\_BS005

Page 52 of 64

- Treatment-related TEAEs according to the Principle Investigator (IAWK12, IAWK24 and FPA)
- Procedures-related TEAEs (FPA Only)
- Serious treatment-related TEAEs (IAWK12, IAWK24 and FPA)
- TEAEs leading to IMP discontinuation (IAWK12, IAWK24 and FPA)
- TEAEs leading to IMP interruption
- TEAEs of special interest (IAWK12, IAWK24 and FPA)
- IRRs (IAWK12, IAWK24 and FPA)

The overview table will also include a 95% Agresti-Min CI (in case <30 participants in each group) or a 95% Newcombe CI (in case of >30 participants in each group) CI for the difference in AE rate between efgartigimod and placebo.

The event rate per 100 PYFU is defined as 100 \* the number of events divided by the sum of the follow-up time during which an event is considered treatment-emergent of all participants per treatment arm expressed in years (i.e. divided by 365.25).

All AEs, including pretreatment events will be listed.

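### Protocol Section 10.3.3 gives two unreconciled causality standards, so the two-way related/not related flag has no clear answer for some AEs that POTS could explain

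*Protocol*

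**What the plan says.** The causality part of Protocol Section 10.3.3 allows two answers for each AE, related or not related. It then describes how to choose in two ways.

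- **General standard.** The investigator uses clinical judgment to "determine whether there is reasonable possibility that the IMP caused the AE". This is glossed as meaning that "there are facts, evidence, and/or arguments to suggest a causal relationship, rather than a relationship cannot be ruled out". A separate bullet has other causes and the timing of the event taken into account.
- **Labelled definitions.** For the label Related, the text reads: "means that the AE cannot be explained by the participant's medical condition, other therapies, or an accident". It also asks for compelling timing, a response pattern already known or suspected for the drug, or both. For the opposite label, the text reads: "means that the AE can be readily explained by other factors such as the participant's underlying medical condition, concomitant therapy, or accident". It also asks that no link in time or biology be plausible.

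SAP Section 18.1 carries the investigator's two-way answer into the analysis. Treatment-related and serious treatment-related TEAEs appear in the overview table at both interim analyses and the final analysis, and SAP Section 18.1.1 tabulates both by SOC and PT. Protocol Section 9.3.1 has all AEs summarized by relatedness and counts a missing relationship as related. Section 10.3.3 also makes causality one of the criteria for regulatory reporting.

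**The concern.** Under the general standard, another possible cause is one consideration among several. Under the labelled Related definition, it is a bar. Two careful investigators could record opposite answers for the same event, depending on which bullets they follow. The labelled definitions carry the same names as the two recorded values, so a site could easily go by them alone.

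The population makes the conflict practical. Inclusion criterion 3.c requires symptoms from two lists, one of which reads: "Sympathetic over-compensation symptoms: palpitation, heat intolerance, nausea with or without vomiting, insomnia, anxiety, lack of appetite, chest pain, and diaphoresis". Several of these could equally be reported as reactions to an infusion. For such an event the disease is nearly always available as an alternative explanation, and that is the circumstance in which the two standards part.

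At stake is the meaning of the treatment-related tables in a study where safety is a primary objective and the drug is new to this population, together with reporting decisions that take causality into account.

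**Working it through.** The plan gives no figure to reproduce. The check is a comparison of wording, followed by a trace of where the flag is used.

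**Step 1. One event against each test.** Take palpitations that begin during an infusion and are worse than the participant's condition would be expected to produce, so that they are collected as an AE. Suppose the investigator finds that the timing and pattern amount to evidence for the IMP.

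| Test in Section 10.3.3 | What it needs | Result |
|---|---|---|
| General standard | Evidence or argument for causation, alternatives weighed | Met, by supposition |
| Related | No explanation from the condition, other therapies or an accident; plus compelling timing and/or a recognised pattern | Not met: POTS can explain it |
| Not related | Readily explained by other factors; plus no plausible temporal or biologic link | Not met: the timing is plausible |

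**Step 2. All combinations.** Treat the two sentences of each labelled definition as both required, and simplify each element to yes or no.

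| Other explanation | Link to IMP | Labelled definitions give |
|---|---|---|
| No | Yes | Related |
| Yes | No | Not related |
| Yes | Yes | Neither |
| No | No | Neither |

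Two of the four cells have no answer. The general standard settles both: the third row goes by the weight of evidence, and the fourth is not related because nothing suggests causation. Timing that is plausible but not compelling widens the gap further. If the two sentences of Not related were instead read as alternatives, the third row would become Not related. The gap there would close, but the labelled definition would then contradict the general standard outright.

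**Step 3. Overlap with the disease.** Criterion 3.c lists 7 + 8 = 15 symptoms and requires at least 3 from each list, so every participant enters with at least 3 + 3 = 6. This counts eligibility features. It does not count AEs affected.

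**Step 4. Where the flag is used.**
- Uses the investigator's flag: treatment-related and serious treatment-related TEAEs, the Protocol Section 9.3.1 summary by relatedness, and reporting decisions that use causality.
- Does not use it: the primary safety endpoints (incidence and severity of AEs, SAEs, laboratory, vital sign and ECG changes); tables of all, serious and grade 3 or higher TEAEs; AESIs, which are defined by SOC; and infusion-related reactions, which SAP Section 18.1 defines by MedDRA terms and a 48-hour window.
- Uses a different judgment: the relatedness criteria in Protocol Sections 7.1.1 and 7.1.2, which turn on the sponsor's view. No separate definition is given for the sponsor.

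**Step 5. Weight of one participant.** With 42 randomized 2:1, the arms are 42 × 2/3 = 28 and 42 × 1/3 = 14. One reclassified participant moves the treatment-related incidence by 1/28 = 3.6 percentage points on efgartigimod, or 1/14 = 7.1 points on placebo. The documents do not say how many events would fall in the gap, so these weights cannot be turned into an expected error.

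**The case against.** The strongest reply is that the practical reach is small.

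- The general standard is not loose. It asks for positive evidence and says that failure to rule a link out is not enough. In a participant with ongoing palpitations, timing alone may not suffice. This stands, and it narrows the gap between the tests. It does not remove the gap, because an event with real evidence for the IMP still meets neither labelled definition.
- Section 10.3.1 keeps expected disease symptoms, and ordinary fluctuations that do not worsen, out of AE collection. Overlapping events that are collected have already been judged worse than expected, which weakens the disease as an explanation. This stands as a limit on volume.
- The same wording is applied under blind in both arms, and the primary safety endpoints do not depend on it. Both points are correct.
- Missing relatedness is counted as related. That does not correct a recorded answer of not related.

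Two stronger readings are tempting. A reader might infer that drug-related counts are driven towards zero. The documents do not show this: an event in the gap is undefined, and an investigator relying on the general standard could record it as related. A reader might also infer that the discontinuation criteria would be triggered too rarely. That does not follow either. Those criteria use the sponsor's judgment, Section 7.1.2 lists reasons that may apply, and Section 7.1.1 has routes that need no relatedness call: the investigator's decision, an AE that the investigator considers a contraindication, and most new or recurrent malignancies.

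Extending the point to infections is also weak. Ordinary exposure is not among the causes named under Related, and infections are counted as AESIs whether related or not.

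**Conclusion.** The inconsistency is real, and nothing else in the protocol or SAP resolves it. Section 10.3.3 contains two causality standards that can disagree, and its labelled definitions do not cover every case although the answer is binary. Investigator-assessed treatment-related and serious treatment-related TEAE counts, and reporting decisions that use causality, may therefore be inconsistent between sites. Where the Related bullet is read literally, they may be too low.

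The size cannot be estimated, and a downward shift is a risk rather than a demonstrated bias. The conclusion assumes that some collected AEs have both a possible disease explanation and evidence for the IMP, and that at least some sites go by the labelled definitions. The documents make the first plausible and are silent on the second. The sponsor's relatedness judgment lacks a stated standard, but no effect on discontinuation is shown. This is a clarification worth making, and it does not threaten the primary safety analysis.

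**What to change.** Reduce Section 10.3.3 to one exhaustive test by rewriting the two labelled bullets to match the general standard:

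- Related: there is a reasonable possibility that the IMP caused the AE.
- Not related: there is no reasonable possibility that the IMP caused the AE.

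Keep the existing gloss on reasonable possibility. Keep the bullet on alternative causes and timing, so that these are weighed and are not a bar. Add a sentence stating that the same standard applies where Sections 7.1.1 and 7.1.2 refer to the sponsor's relatedness judgment, leaving the discontinuation rules themselves unchanged.

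The cost is two rewritten bullets, one added sentence, and matching eCRF and site guidance. The SAP tables need no change. The downside is that somewhat more AEs may be flagged as related, under blind and in both arms.
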